10 STATISTICAL CONSIDERATIONS

10.1 Study Hypotheses

FDA guidance document suggests using a reduced PK design for drugs that are predominantly metabolized or secreted in the bile [38]. In a reduced PK study design, the trial compares PK in patients with normal renal function and to patients with severe renal impairment and patients with ESRD not yet on dialysis. If the reduced PK study shows at least a 50% increase in AUC in patients with severe renal impairment and patients with ESRD not yet on dialysis relative to the matched healthy controls, a “full” renal impairment study in patients with all intermediate levels of renal function impairment should be conducted [38]. Otherwise, no further study is recommended.

In the current study, Part A is considered the reduced PK study in which the geometric mean ratio of AUC (AUC_{last} and area under the plasma concentration-time curve from time zero to infinity [AUC_{∞}]) will be determined comparing Group 2 participants (Severe renal impairment and ESRD, not on dialysis) to matched Group 1A participants (healthy participants with normal GFR). The ratio of geometric mean AUCs and 90% confidence interval (CI) of the parent compound will be considered in determining whether to continue with a full renal impairment study (enrollment of subsequent cohorts in Part B). Interim PK data of the parent compound will be reviewed by some members of the study team from DMID and TB Alliance before decision is made to proceed to Part B. For further details, please refer to the PK Manual.

[figure not shown]
In Part B, the primary intent will be to estimate PK parameters of the parent compound and metabolites and model the relationship between measures of renal function and the PK parameters to determine whether dosage adjustment is required for patients with impaired renal function. Estimates and CIs will be utilized rather than formal hypothesis tests.

No formal hypothesis tests are planned for safety analyses, but safety data will be collected and analyzed.

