3 STUDY OBJECTIVES AND ENDPOINTS

3.1 Study Objectives

3.1.1 Primary Study Objective

- To evaluate the PK profiles of pretomanid in plasma and urine after a single oral dose of 200 mg in participants with renal impairment compared to matched healthy controls.

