6 GENERAL STATISTICAL CONSIDERATIONS

6.1 General Principles

There are several units of analysis in this study. For the PK analysis, the unit of analysis will be the reported pretomanid concentrations, however, PK profiles in both plasma and urine will be evaluated at the participant level. Medical history, concomitant medications, AEs, SAEs, clinical laboratory, physical examination (PE), vital signs, and ECG will be presented at the participant level, and summaries will be presented at the study and renal impairment group level.

All continuous variables will be summarized using the following descriptive statistics: n (non-missing sample size), arithmetic mean, standard deviation (SD), median, minimum (min), and maximum (max). PK concentration and parameter summaries will additionally report the geometric mean (GM) and coefficient of variation (CV). Minima and maxima will be reported to the same precision as the raw values, means and medians will be presented to one extra decimal place than the raw values and standard deviations will be reported to 2 extra decimal places than the raw values.

The frequency and percentages (based on the non-missing sample size) of observed levels will be reported for all categorical measures. Percentages will be rounded to one decimal place (i.e. XX.X%) except for 100% which will be reported with no decimal places. In general, all data will be listed, sorted by impairment group and participant, and when appropriate by visit number and parameter within participant. In general, the last recorded value prior to study drug administration will be considered as baseline. Changes from baseline will be calculated as the follow-up visit value minus the corresponding baseline value. All summary tables will be structured with a column or row block for each impairment group in the order (Mild Renal Impairment, Moderate Renal Impairment, Severe Renal Impairment, Matched Controls) and will be annotated with the total population size relevant to that table/impairment group, including any missing observations. More details will be provided for reporting pharmacokinetic results in Section 10.

Estimates and CIs will be utilized rather than formal hypothesis tests.

No formal hypothesis tests are planned for safety analyses, but safety data will be collected and analyzed.

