10.2.3 Comparison of Impairment Groups

If at least one matching participant in the healthy volunteer group is available in the renal impairment groups, the following random effects ANOVA model will be used to test for a group by site interaction and if significant ($p < 0.10$), estimate group and site level parameters and compare impairment groups for primary PK parameters:

$$Y_{ij} = \mu + \tau_{[ij]} + \alpha_i + \gamma_k + \tau_{[ij]}\gamma_k + \varepsilon_{ij}$$

Here, i represents the matched block, j represents the participant in matched block i , Y_{ij} is the log-transformed PK parameter for participant j in block i , $\tau_{[ij]}$ is the impairment group effect for the group in which

participant j in block i belongs, α_i is the random group effect for matched block i , γ_k is the indicator variable for the fixed effect of study site k , and $\tau_{[ij]}\gamma_k$ is the interaction between participant impairment group and site. If no matching participants are available with PK parameters, the standard fixed effects ANOVA model without random effect α_i will be used. The following SAS code may be used to estimate the model above:

```
proc mixed data=impairment;
  class match group (ref="Matched Control") site;
  model logPKpar = group site group*site / solution cl alpha=0.10;
  random match;
  lsmeans group site group*site;
  run;
```

The estimates from this model can be exponentiated to get fold differences.

If the group by site interaction is not significant then the following model will be used to estimate group level parameters:

$$Y_{ij} = \mu + \tau_{[ij]} + \alpha_i + \gamma_k + \varepsilon_{ij}$$

The following SAS code may be used to estimate the model above:

```
proc mixed data=impairment;
  class match group (ref="Matched Control") site;
  model logPKpar = group site / solution cl alpha=0.10;
  random match;
  lsmeans group;
  run;
```

The estimates from this model can be exponentiated to get fold differences.

Pairwise fold differences in drug exposure will be calculated to compare each of the mild, moderate, and severe renal impairment groups with healthy controls. Fold difference and mean will be estimated by ANOVA and shown using 90% confidence intervals. An adjustment to the confidence level for multiple comparisons is not planned ([Table 92](#)).

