Site	Impairment Group	Statistic	AUC _{last} (μg*h/mL)	AUC _∞ (μg*h/mL)	C _{max} (μg/mL)
All Sites	Mild	Mean			
		90% CI of Mean			
		Fold Change ^a			
		90% CI of Fold Change			
	Moderate	Mean			
		90% CI of Mean			
		Fold Change ^a			
		90% CI of Fold Change			
	Severe	Mean			
		90% CI of Mean			
		Fold Change ^a			
		90% CI of Fold Change			
	Matched Controls	Mean			
		90% CI of Mean			
Alliance for Multispecialty Research	Mild	Mean			
		90% CI of Mean			
		Fold Change ^a			
		90% CI of Fold Change			
	Moderate	Mean			
		90% CI of Mean			
		Fold Change ^a			
		90% CI of Fold Change			
	Severe	Mean			
		90% CI of Mean			
		Fold Change ^a			
		90% CI of Fold Change			
	Matched Controls	Mean			

Table 93: Estimated Impairment Group Fold Change for Noncompartmental PK Parameters (continued)

		90% CI of Mean			
Advanced Pharma	Mild	Mean			
		90% CI of Mean			
		Fold Change ^a			
		90% CI of Fold Change			
	Moderate	Mean			
		90% CI of Mean			
		Fold Change ^a			
		90% CI of Fold Change			
	Severe	Mean			
		90% CI of Mean			
		Fold Change ^a			
		90% CI of Fold Change			
	Matched Controls	Mean			
		90% CI of Mean			

Notes: ^a Comparison is to matched controls.

Table 94: Estimated Impairment Group Shift for Noncompartmental PK Parameters

[Implementation Note: Site column will only be included if confidence intervals between sites do not overlap.]

Site	Impairment Group	Statistic	T _{max} (h)
All Sites	Mild	Median	
		90% CI of Median ^a	
		Shift ^b	
		90% CI of Shift ^a	
	Moderate	Median	
		90% CI of Median ^a	
		Shift ^b	
		90% CI of Shift ^a	
	Severe	Median	
		90% CI of Median ^a	
		Shift ^b	
		90% CI of Shift ^a	
	Matched Controls	Median	
		90% CI of Median ^a	
Alliance for Multispecialty Research	Mild	Median	
		90% CI of Median ^a	
		Shift ^b	
		90% CI of Shift ^a	
	Moderate	Median	
		90% CI of Median ^a	
		Shift ^b	
		90% CI of Shift ^a	
	Severe	Median	
		90% CI of Median ^a	
		Shift ^b	
		90% CI of Shift ^a	
	Matched Controls	Median	
		90% CI of Median ^a	
Advanced Pharma	Mild	Median	
		90% CI of Median ^a	
		Shift ^b	
		90% CI of Shift ^a	

Table 94: Estimated Impairment Group Shift for Noncompartmental PK Parameters (continued)

	Moderate	Median	
		90% CI of Median ^a	
		Shift ^b	
		90% CI of Shift ^a	
	Severe	Median	
		90% CI of Median ^a	
		Shift ^b	
		90% CI of Shift ^a	
	Matched Controls	Median	
		90% CI of Median ^a	

Notes:
^aConfidence limits will be estimated using the inverted rank score method.
^bComparison is to matched controls.

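### If Part B runs, the SAP 10.2.3 model sets each renal group against all pooled controls with no cohort term, so the final severe fold change does not rest on Group 1A alone

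*SAP*

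**What the plan says.** The protocol defines three control cohorts, each matched to one renal group: 1A to Group 2 (severe), 1B to Group 3 (mild) and 1C to Group 4 (moderate). The primary objective (SAP 3.1.1) is to evaluate pretomanid PK "in participants with renal impairment compared to matched healthy controls". For Part A, Protocol 10.1 says that the geometric mean AUC ratio "will be determined comparing Group 2 participants (Severe renal impairment and ESRD, not on dialysis) to matched Group 1A participants".

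The final analysis is organised differently. SAP 6.1 sets out every summary table "in the order (Mild Renal Impairment, Moderate Renal Impairment, Severe Renal Impairment, Matched Controls"), so there are four groups and the controls are one of them. Both PROC MIXED models in SAP 10.2.3 carry the same coding, "class match group (ref='Matched Control') site", with a random term that "is the random group effect for matched block". The text then says: "Pairwise fold differences in drug exposure will be calculated to compare each of the mild, moderate, and severe renal impairment groups with healthy controls". The fold-change shell (Table 93 in Appendix 1, cited as Table 92 in the text of 10.2.3) has a single control row per site and the footnote "Comparison is to matched controls".

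No contrast of 2 vs 1A, 3 vs 1B or 4 vs 1C is written for the final analysis, and neither document says that the control cohorts are pooled.

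**The concern.** Matching each control cohort to its own renal group protects the comparison when the renal groups differ in age, sex or race. A single control level gives up part of that protection. The severe group is compared partly with controls chosen to resemble mild and moderate patients and enrolled later, because 1B and 1C open only after the Part A review. The model has no age, cohort or period term to absorb such differences.

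If the cohorts differ in mean AUC for reasons other than renal function, part of that difference enters the reported fold change. It can inflate or hide a renal effect. Protocol 10.1 says the Part B results will inform whether dosage adjustment is required. The final severe fold change would also differ in definition from the Group 2 vs 1A ratio used for the Part A decision, without the SAP saying so.

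**Working it through.** **Inputs.** Six participants per group, so 18 controls. CV 20% for AUC, so log SD s = √ln(1 + 0.20²) = 0.198. Observed ratio 2, no correlation between matched pairs, 90% CI (Protocol 10.2, SAP 5). Model terms from SAP 10.2.3.

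**1. The plan's own Part B interval.** CI = 2 × exp(± t × s × √(1/n₁ + 1/n₂)).

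- 6 vs 18, df 22: s√(1/6 + 1/18) = 0.0934, t = 1.717, CI (1.704, 2.348). This is the stated (1.70, 2.35).
- 6 vs 6, df 10: s√(2/6) = 0.1143, t = 1.812, CI (1.63, 2.46).
- 6 pairs, df 5: CI (1.59, 2.52).
- 6 vs 12, df 16: CI (1.68, 2.38).

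The stated interval matches 18 pooled controls. The Part A figure does not: the probability of about 70% that the lower bound reaches 1.5 is reproduced by six pairs on 5 df (noncentrality ln(2/1.5)/0.1143 = 2.516, giving 69.7%). Two independent groups of six on 10 df give 75.7%. So the two planning figures appear to rest on different comparators.

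**2. Which controls the final severe estimate uses.** Take 18 one-to-one pairs, four group levels, a random block with within-pair correlation ρ, and no site term. The generalised least squares solution on the log scale is

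severe effect = mean(Group 2) − ρ × mean(1A) − (1 − ρ) × mean(all 18 controls).

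The mean of all controls gives 1A a weight of one third, so the total weight on 1A is ρ + (1 − ρ)/3 = 1/3 + 2ρ/3. The rest falls on 1B and 1C.

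| ρ | weight on 1A | weight on 1B + 1C |
|---|---|---|
| 0 | 33% | 67% |
| 0.3 | 53% | 47% |
| 0.5 | 67% | 33% |
| 0.8 | 87% | 13% |

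**3. What a cohort difference does.** Suppose there is no renal effect but the severe cohort, patients and controls alike, has 20% higher AUC than the other two. This shift is an assumption; the documents give no cohort effect. With ρ known, the spurious fold change is 1.2 to the power of the weight on 1B + 1C: 1.2^0.667 = 1.13, 1.2^0.467 = 1.09 and 1.2^0.333 = 1.06 at ρ = 0, 0.3 and 0.5.

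In practice REML estimates the block variance. That estimate cannot fall below zero, so at low ρ it puts somewhat more weight on the own controls on average. Simulating the model with REML (no site term, CV 20%) gives 1.11, 1.08 and 1.06. The nominal 90% interval then misses the true ratio of 1 in about 28%, 23% and 19% of trials, while the own-cohort interval stays near 10%. With equal cohort means the pooled interval misses in 10–11%, as it should. At ρ = 0 the block variance is estimated as zero in about half of trials, and the analysis is then a plain 6 vs 18 comparison.

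**4. Price of an own-cohort estimate.** With a residual pooled over the 18 pairs (18 − 3 = 15 df) and ρ = 0: t = 1.753, 1.753 × 0.1143 = 0.200, CI = 2 × exp(± 0.200) = (1.64, 2.44).

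**The case against.** The strongest defence is that pooling looks deliberate. The stated Part B precision matches 6 vs 18, and if the control means are equal, pooling is unbiased and more precise (standard error 0.093 against 0.114 at ρ = 0). All controls share the same healthy-participant eligibility criteria, dose and fed state. Protocol 2.1.5.2 reports no clinically significant PK differences by sex, body weight or race, which weakens two of the matching factors as a source of cohort differences. All of this stands. It leaves age, which is a matching factor not on that list, and enrolment period. The documents show no effect of either, and they do not rule one out.

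Several stronger readings are tempting but not supported:

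- A reader might infer that the Part A decision is compromised. It is not: 1A is then the only control group, so all the control weight falls on it.
- A reader might infer that Protocol 10.1 fixes Group 2 vs 1A as the final severe contrast. That sentence concerns Part A. The objective names matched healthy controls without naming 1A.
- A reader might infer that the matching is ignored. The random block keeps part of it, and more as ρ rises.
- A reader might treat this as an inflated error rate of a planned significance test. Group differences are to be reported as estimates and CIs only.
- A reader might also blame pooling for sensitivity to unequal spread between groups. That comes mainly from the common-variance assumption, which the own-cohort model with a pooled residual shares.

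**Conclusion.** The point holds in a limited form. If Part B runs, the final severe fold change mixes its own matched controls with those of the other two groups, and at the SAP's planning assumption only a third of the control weight is on 1A. The same applies to the mild and moderate contrasts. The bias is zero if the three control cohorts share a mean. For an assumed 20% cohort shift it is 6–11% at ρ between 0.5 and 0, which is modest beside the 50% increase used for the Part A decision but enough to spoil the coverage of the 90% interval.

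Pooling is a defensible trade of bias against precision, so replacing it outright is not called for. What is missing is a statement that it is done and a matched estimate beside it. The exact weights assume one-to-one pairs and no site term. Fitting the site effect, or sharing a control between renal participants as SAP 4.4.3 allows, would change them.

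**What to change.** - In SAP 10.2.3 and the footnote to the fold-change table, state that the existing estimate pools all controls from 1A, 1B and 1C.
- Add a second version of the model with a fixed cohort factor (1A+2, 1B+3, 1C+4), keeping the random matched block. With that term each group coefficient becomes the contrast within its own cohort. Report 2 vs 1A, 3 vs 1B and 4 vs 1C with 90% CIs in rows beside the pooled estimates.
- Assign any control matched to more than one renal participant (SAP 4.4.3) to the cohort in which it was enrolled.
- In SAP 5 and Protocol 10.2, state that (1.70, 2.35) corresponds to 6 vs 18 pooled controls, and give about (1.64, 2.44) for the own-cohort contrast with a pooled residual on 15 df.

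The cost is some wording, one model term and a few table rows. No new data are needed, and the pooled estimate keeps its planned precision.

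### When the group-by-site interaction is kept, the SAP's code prints a fold difference with a 90% CI for the reference site only, and neither code block prints the 90% CI of the group means

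*SAP*

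**What the plan says.** SAP 10.2.3 (Comparison of Impairment Groups) sets the required output: "Fold difference and mean will be estimated by ANOVA and shown using 90% confidence intervals". The fold-change shell in SAP Appendix 1, section 14.6 (Table 93; the text of 10.2.3 cites it as Table 92) has rows for the mean, its 90% CI, the fold change and "90% CI of Fold Change". There is an All Sites block, plus one block per site if the interaction has p<0.10. The Protocol Summary gives two sites.

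The code is introduced with "The following SAS code may be used to estimate the model above". In the interaction block:

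- CLASS is "class match group (ref='Matched Control') site": a reference level for group, none for site.
- MODEL is "model logPKpar = group site group*site / solution cl alpha=0.10", so the 90% limits are requested for the model coefficients.
- LSMEANS is "lsmeans group site group*site", with no options.

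The no-interaction block drops the interaction term and uses "lsmeans group", again with no options. Neither block has an ESTIMATE, CONTRAST or SLICE statement. After each block the SAP says: "The estimates from this model can be exponentiated to get fold differences". It does not say which estimates.

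**The concern.** The same exponentiation sentence follows both models, but a group coefficient means different things in the two. Without the interaction it is the group-versus-control difference common to both sites. With the interaction it is that difference at one site, and the SAP does not fix which site that is.

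This is the planned comparison for the primary PK parameters. In the interaction branch, an analyst who exponentiates the one group contrast that comes with a 90% CI would enter a single site's ratio, from part of the data, as the All Sites result. The rows for the 90% CI of the mean have no printed source in either branch.

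**Working it through.** The plan states no figure on this point, so there is none to reproduce. The check is what each printed quantity estimates, followed by a numerical illustration.

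**Inputs from the documents.** Two sites (Protocol Summary); 6 per group and a CV of 20% for AUC, with prior studies at 16% to 33% (SAP 5); interaction kept at p<0.10 (SAP 10.2.3).

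**Assumptions.** Two groups, as in Part A; matched pairs within site, three pairs per site; fold differences of 1.2 at site A and 2.0 at site B; site B sorts last. Standard errors and 8 degrees of freedom come from ordinary least squares. The random match effect cancels in within-pair contrasts, so it does not alter which contrast a row estimates, though it may alter the precision and degrees of freedom. What PROC MIXED prints is general software knowledge, not something the documents state.

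**Contrasts.** On the log scale, let b1 be the group coefficient and b3 the interaction coefficient for site A, with site B as reference.

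- Site B difference = b1 = ln 2.0 = 0.693
- b3 = ln(1.2/2.0) = −0.511
- Site A difference = b1 + b3 = ln 1.2
- All Sites LS-mean difference = b1 + b3/2 = 0.693 − 0.255 = 0.438, so the fold is 1.55 = √(1.2 × 2.0)

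**Standard errors.** Log SD = √ln(1 + 0.20²) = 0.198. One site: 0.198 × √(2/3) = 0.162. All Sites: 0.198 × √(2/6) = 0.114. The ratio is 1.41. Limits use t = 1.860.

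| Quantity | Fold | 90% CI | Printed with a CI? |
|---|---|---|---|
| Group row (site B) | 2.00 | 1.48 to 2.70 | Yes |
| All Sites LS-mean difference | 1.55 | 1.25 to 1.92 | No |
| Site A difference | 1.20 | 0.89 to 1.62 | No |
| Interaction row | 0.60 | 0.39 to 0.92 | Yes, but it is a ratio of ratios |

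If site A sorted last, the group row would be 1.20. With unequal splits, the one-site and All Sites standard errors are 0.198 and 0.121 (two pairs at the reference site, four at the other), or 0.140 and 0.121 (four and two).

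**Is the branch reached?** Here the interaction gives t = 0.511/(0.198 × √(4/3)) = 0.511/0.229 = 2.23, above 1.860, so it is kept. At a CV of 33% the log SD is 0.3215 and t = 0.511/(0.3215 × √(4/3)) = 1.38, p about 0.21, so it would be dropped. In simulation with no true interaction (CV 20%, 10,000 runs at each of four true folds from 1.3 to 2.0), the rule kept the interaction in about 10% of runs. In those runs the group row and the All Sites estimate differed by a median factor of about 1.24.

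**Without the interaction.** On the same data the group row gives 1.55, equal to the LS-mean difference, and its 90% CI is the one required.

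**Means, both blocks.** LSMEANS without CL prints the estimate, SE, df, t and p, but no limits. ALPHA on MODEL does not carry over to LSMEANS. The intercept's 90% CI is for controls at the reference site, not for a group mean.

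**The case against.** The case for leaving the text alone is substantial.

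- The code is offered as something that may be used. The binding sentence and the table shell ask for the right quantities. One coefficient per group cannot fill three different fold-change blocks, so a programmer completing the shell would have to add options.
- The exponentiation sentence does not name the SOLUTION coefficients. The same block requests group and group-by-site LS-means, and exponentiated differences between those are the correct folds.
- Point estimates follow by subtracting printed LS-means, and a CI for each mean from its SE and df.
- The site ratios and the split are assumptions, and at the upper CV the same ratios would not keep the interaction.

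All of this stands as a limit on the point. It does not remove it. Exponentiated LS-means are geometric means, not fold differences, and without DIFF the standard error of a difference is not printed. The LS-means share the match effect, so it cannot be formed from their separate standard errors. On either reading, the interaction block does not yield the All Sites fold change with its 90% CI.

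A reader might also infer that the Part A decision, with its threshold of a 50% AUC increase, could turn on site order. The documents do not support that. SAP 6.2 and 6.6 exclude hypothesis testing from the interim review, while this branch is entered only through a p<0.10 test. Protocol 10.1 refers the interim PK details to a PK Manual that is not among the documents.

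**Conclusion.** The point holds, in two parts of different scope. In the interaction branch only, the sole group-versus-control contrasts printed with a 90% CI belong to the last-sorted site, and exponentiating them does not give the All Sites fold change or the other site's. In both branches, the 90% CI of the means is not printed. Fold differences and their 90% CIs are correct when the interaction is dropped.

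The size depends on how far the sites differ: 2.00 or 1.20 against 1.55 in the example, with a standard error 1.41 times larger at three pairs per site. Those figures rest on the assumed ratios, the equal split and a 20% CV; the contrast algebra does not.

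A reader might go further and infer that the plan will report a wrong primary result. That is not shown, because the code is permissive and the required output is correctly described. It is a fault in the specification that should be corrected before the final analysis.

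**What to change.** In the interaction block, use `lsmeans group / diff=control('Matched Control') cl alpha=0.10;` for the All Sites rows. Keep the group-by-site means with `lsmeans group*site / diff cl alpha=0.10;`, using only the within-site differences from control, or obtain those differences with SLICE or ESTIMATE statements within site. Table 93 needs these for its site-level means and fold changes.

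In the no-interaction block, add `cl alpha=0.10` to the LSMEANS statement. The 90% level must be stated there, because CL alone would give 95% limits. DIFF is not needed in this block.

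Keep the exponentiation instruction in both branches. In the interaction branch, say that it applies to the LS-means (geometric means), the LS-mean differences (fold differences) and their limits, and not to the SOLUTION coefficients.

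The cost is a few lines of SAP text and code. No data collection, sample size or table layout changes.
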